6.2.2.3 Classification of an Adverse Event

Relationship of an AE to investigational product will be assessed as follows:

- **Definite:** There is a clinically plausible time sequence between the onset of the AE and the administration of investigational product; when the event responds to withdrawal of investigational product and/or recurs with re-administration of investigational product
- **Probable:** There is a clinically plausible time sequence between the onset of the AE and the administration of investigational product; the AE is unlikely to be caused by the concurrent/underlying illness, other drugs or procedures
- **Possible:** There may or may not be a clinically plausible time sequence between the onset of the AE and the administration of investigational product and a cause cannot be ruled out
- Unrelated: There is not a temporal or causal relationship to investigational product administration

The investigator is responsible for evaluating all AEs and determining the severity of the event. Severity will be categorized as mild, moderate, or severe according to the following definition:

- **Mild:** Event may be noticeable to subject; does not influence daily activities; usually does not require intervention
- **Moderate:** Event may be of sufficient severity to make a subject uncomfortable; performance of daily activities may be influenced; intervention may be needed
- Severe: Event may cause severe discomfort; usually interferes with daily activities; subject may not be able to continue in the study; treatment or other intervention usually needed

Expectedness

The Sponsor medical monitor will be responsible for determining whether an adverse event (AE) is expected or unexpected. An AE will be considered unexpected if the nature, severity, or frequency of the event is not consistent with the risk information previously described for the study intervention. Expectedness is further defined in the Investigator's Brochure (IB) under Anticipated Risks and Side Effects. The list of AEs found in the IB can be considered to be expected AEs.

6.2.2.4 Time Period and Frequency for Event Assessment and Follow-Up

The occurrence of an adverse event (AE) or serious adverse event (SAE) may come to the attention of study personnel during study visits and interviews of a study participant presenting for medical care, or upon review by a study monitor.

All AEs including local and systemic reactions not meeting the criteria for SAEs will be captured on the appropriate case report form (CRF). Information to be collected includes event description, time of onset, clinician's assessment of severity, relationship to study product (assessed only by those with the training and authority to make a diagnosis), and time of

resolution/stabilization of the event. All AEs occurring while on study must be documented appropriately regardless of relationship. The investigator will assess subject post-treatment and at each subsequent study visit for the occurrence of AEs. All AEs will be followed to adequate resolution.

Any medical condition that is present at the time that the participant is screened will be considered as baseline and not reported as an AE. However, if the study participant's condition deteriorates at any time during the study, it will be recorded as an AE.

Changes in the severity of an AE will be documented to allow an assessment of the duration of the event at each level of severity to be performed. AEs characterized as intermittent require documentation of onset and duration of each episode.

The investigator should follow the SAE until it resolves or is determined by the investigator to be stable, or the subject is lost to follow-up. The investigator should continue to report any significant follow-up information to the sponsor or the authorized representative, and the IRB, up to the point the event has resolved, or is determined to be stable. Resolution means the subject has returned to the baseline state of health, and stable means the investigator does not expect any further improvement or worsening of the subject's condition.

Any new SAEs reported by the subject to the investigator that occur after the last scheduled contact and are determined by the investigator to be reasonably associated with the administration of investigational product should be reported to the sponsor or the authorized representative, and the IRB, as required.

6.2.2.5 Adverse Event Reporting

The Investigator will assess subjects for post-treatment AEs at each subsequent trial visit. In order to avoid bias in eliciting AEs, subjects should be asked the following non-leading question: "How have you felt since your last visit?" All AEs (serious and non-serious) reported by the subject must be recorded on the source documents and CRFs. Adverse events related to COVID19 should be documented.

6.2.2.6 Serious Adverse Event Reporting

An Investigator must report an SAE to Revance or the designated CRO representative within **24 hours** of their awareness of the event:

- 1. Complete and return an SAE Form with all information known to date; including the Investigator's assessment of causality.
- 2. A fatal or life-threatening SAE must be telephoned to Revance or the authorized representative as soon as the Investigator learns of the event.
- 3. All pertinent medical records (discharge summary, autopsy report, etc.) should be obtained and judgments of all medical personnel who assisted in subject's treatment and follow-up.
- 4. Provide follow-up information to Revance or the authorized representative.

All SAEs will be followed until satisfactory resolution or until the Investigator deems the event to be chronic or the participant is stable. Other supporting documentation of the event may be requested by the Data Coordinating Center (DCC)/study sponsor and should be provided as soon

as possible. The study sponsor will be responsible for notifying the FDA of any unexpected fatal or life-threatening suspected adverse reaction as soon as possible, but in no case later than 7 calendar days after the sponsor's initial receipt of the information. In addition, the sponsor must notify FDA and all participating investigators in an Investigational New Drug (IND) safety report of potential serious risks, from clinical trials or any other source, as soon as possible, but in no case later than 15 calendar days after the sponsor determines that the information qualifies for reporting. Regulatory authorities, IRBs, and Investigators will be notified of SAEs in accordance with applicable regulations and requirements (e.g., GCPs, ICH Guidelines, national regulations and local requirements).

6.2.2.7 Reporting Events to Participants

Revance will disclose clinical trial data to individuals, to investigators at clinical sites, and publicly as aggregate summaries, in accordance to Regulatory and local legal requirements.

Follow-up of Non-Serious Adverse Events

Non-serious AEs that are identified during the last scheduled trial visit (or early discontinuation, if applicable) must be recorded on the AE CRF as ongoing.

Any clinically significant abnormal test results, e.g., laboratory findings, at the Week 12/Early Termination visit should be followed to resolution or until determined by the Investigator to be stabilized. Repeat tests may be indicated to establish this. If a subject has any clinically significant, trial-related abnormalities at the end of the trial, the Medical Monitor should be notified, and every effort made by the Investigator to arrange follow up evaluations at appropriate intervals to document the course of the abnormalities.

Follow-up of Post-Trial Serious Adverse Events

SAEs that are identified on the last scheduled contact (or early discontinuation, if applicable) must be recorded on the AE CRF page and reported to the CRO and Revance according to the reporting procedures outlined in Section 6.2.2.6. This may include unresolved previously reported SAEs, or new SAEs. The Investigator should follow these SAEs until the events are resolved, or the subject is lost to follow-up. The Investigator should continue to report any significant follow-up information to the Medical Monitor, Revance, and the IRB up to the point the event has been resolved. Resolution means the subject has returned to the baseline state of health, or the Investigator does not expect any further improvement or worsening of the subject's condition.

Any new SAEs reported by the subject to the Investigator that occur after the last scheduled contact and are determined by the Investigator to be reasonably associated with the administration of investigational product should be reported to Revance and the IRB.

DaxibotulinumtoxinA for Injection for Adult Upper Limb Spasticity

6.3 Injection Site Evaluation:

The injection sites will be evaluated at Injection Visit (Day 1) pre- and post- treatment (to determine if there is an immediate reaction to the investigational product), follow-up visits (Weeks 2, 4, and 36 or Early Termination visit), if applicable. The assessment will be done as a global evaluation of the injection sites to be performed pre-treatment on Injection visit.

Table 5.	Injection Site Evaluation
----------	---------------------------

Assessment Descriptor	Present?	
	Yes	No
Erythema		
Edema		
Burning or Stinging (sensation as described by subject)		
Itching (sensation as described by subject)		
Bruising		
Drainage		

DaxibotulinumtoxinA for Injection for Adult Upper Limb Spasticity	
Protocol 1820203 Amendment 2	

6.4 Reporting of Pregnancy

During the trial, all WOCBP should be instructed to contact the Investigator immediately (within 24 hours) if they suspect they might be pregnant (e.g., missed or late menstrual cycle). The Investigator must immediately notify Revance or designated Contract Research Organization (CRO) of any female subject who becomes pregnant any time during study participation, record the information on the Pregnancy Notification Form and send the form to the CRO. The site will be asked to follow-up with the subject periodically during the pregnancy for ongoing health and safety information through term, as applicable. Subjects will remain on the trial.

6.5 Columbia-Suicide Severity Rating Scale (C-SSRS)

The C-SSRS is a questionnaire that prospectively assesses Suicidal Ideation and Suicidal Behavior using a semi-structured interview to probe subject responses (Posner, 2008) (APPENDIX K). The C-SSRS is to be administered at Screening and each study visit, including unscheduled ones. Both the Baseline/Screening and Since Last Visit versions will be utilized. All assessors will receive formal training in the use of this tool.

A subject who endorses "suicidal ideation" must be referred to a mental health professional for further assessment and/or treatment.

7 UNANTICIPATED ADVERSE EVENTS

7.1 Definition of Unanticipated Adverse Events

Unanticipated problems involving risks to participants or others to include, in general, any incident, experience, or outcome that meets **all** of the following criteria:

Unexpected in terms of nature, severity, or frequency given (a) the research procedures that are described in the protocol-related documents, such as the Institutional Review Board (IRB)-approved research protocol and informed consent document; and (b) the

- Characteristics of the participant population being studied;
- Related or possibly related to participation in the research ("possibly related" means there is a reasonable possibility that the incident, experience, or outcome may have been caused by the procedures involved in the research); and suggests that the research places subjects or others at a greater risk of harm (including physical, psychological, economic, or social harm) than was previously known or recognized.

Revance will comply with these criteria for reporting Unanticipated Adverse Events.

7.2 Unanticipated Adverse Event Reporting

The Investigator will report unanticipated Adverse Events to the reviewing Institutional Review Board (IRB) and the Sponsor. The unanticipated adverse event report will include the following information:

- Protocol identifying information: protocol title and number, PI's name, and the IRB project number.
- A detailed description of the event, incident, experience, or outcome;
- An explanation of the basis for determining that the event, incident, experience, or outcome represents an unanticipated adverse event;

DaxidotulinumtoxinA for injection for Adult Upper Limb Spasticity	Version 6
Protocol 1820203 Amendment 2	xx June 2020

- A description of any changes to the protocol by the Sponsor or other corrective actions that have been taken or are proposed in response to the unanticipated adverse event.
- The Sponsor will update the IB or provide Dear Doctor letter should these actions be deemed required.

To satisfy the requirement for prompt reporting, unanticipated adverse events will be reported using the following timeline:

- Unanticipated adverse events that are fatal and life-threatening serious adverse events (SAEs) will be reported to the IRB and to the Sponsor within seven (7) days of the Investigator becoming aware of the event.
- Any other unanticipated adverse events that are SAEs will be reported to the IRB and to the Sponsor within 15 days of the Investigator becoming aware of the problem.
- All unanticipated adverse events that non-serious AEs are not required to be reported to the IRB or to the Sponsor.
- All unanticipated serious adverse events should be reported to appropriate institutional officials (as required by an institution's written reporting procedures), the supporting agency head (or designee), and the Office for Human Research Protections (OHRP) if applicable.

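### Protocol 7.2 allows 7 or 15 days to report unanticipated SAEs to the sponsor, where 6.2.2.6 allows 24 hours for the same events

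*Protocol*

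**What the plan says.** Protocol 6.2.2.6 gives the general rule: "An Investigator must report an SAE to Revance or the designated CRO representative within 24 hours of their awareness of the event". It adds: "A fatal or life-threatening SAE must be telephoned to Revance or the authorized representative as soon as the Investigator learns of the event". Neither sentence excepts unanticipated events. The same section sets the sponsor's onward limits. An unexpected fatal or life-threatening suspected reaction goes to FDA within 7 calendar days of the sponsor's first receipt. An IND safety report goes to FDA and all participating investigators within 15 calendar days of the sponsor's determination that the information qualifies.

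Protocol 7.2 opens: "The Investigator will report unanticipated Adverse Events to the reviewing Institutional Review Board (IRB) and the Sponsor". Three lines of its timeline matter here:

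- The first gives 7 days, to the IRB and the sponsor alike, for an unanticipated SAE that is fatal and life-threatening.
- The second deals with the remaining serious cases: "Any other unanticipated adverse events that are SAEs will be reported to the IRB and to the Sponsor within 15 days", again counted from the investigator's awareness.
- The third exempts the non-serious cases: "All unanticipated adverse events that non-serious AEs are not required to be reported to the IRB or to the Sponsor".

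Protocol 7.1 defines these events as unexpected, at least possibly related to the research, and suggesting a greater risk than was previously known. On data capture, Protocol 6.2.2.5 says: "All AEs (serious and non-serious) reported by the subject must be recorded on the source documents and CRFs".

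**The concern.** Two sections give one reporter two deadlines for telling one recipient about one event. The longer deadline falls on the events that matter most: by the 7.1 definition, unanticipated SAEs are the unexpected, possibly related ones that point to added risk, and so the ones most likely to need expedited reporting. A site could reasonably treat 7.2 as the specific rule that displaces the general one.

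What is at stake is how soon the sponsor, and then FDA and the other sites, learn of such an event. The sponsor's FDA clock for fatal or life-threatening reactions starts only when the sponsor receives the information, so any delay at the site is added in front of it.

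**Working it through.** The plan gives no combined figure to reproduce. The check has three steps: confirm that the two rules cover the same events, add the stated limits, and examine the non-serious line separately.

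**1. Do the rules cover the same events?**

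| Element | 6.2.2.6 | 7.2 |
|---|---|---|
| Reporter | Investigator | Investigator |
| Recipient | Sponsor or designated CRO | IRB and sponsor |
| Starting point | Investigator's awareness | Investigator's awareness |
| Events | All SAEs | Unanticipated SAEs, a subset of all SAEs |
| Limit, fatal or life-threatening | Immediate telephone call; form within 24 hours | 7 days |
| Limit, other serious | 24 hours | 15 days |

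Every unanticipated SAE falls under both columns. Section 7.2 contains no cross-reference to 6.2.2.6 and does not mention an earlier report.

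**2. How large is the difference?**

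Take 24 hours as 1 day.

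- Extra time to sponsor receipt = 7.2 limit − 6.2.2.6 limit.
  - Fatal or life-threatening: 7 − 1 = 6 days. This uses the 24-hour limit as comparator and does not credit the earlier telephone call.
  - Other serious: 15 − 1 = 14 days.
- Latest time from awareness to FDA = limit to sponsor + sponsor's limit to FDA.
  - Fatal or life-threatening: 1 + 7 = 8 days under 6.2.2.6; 7 + 7 = 14 days under 7.2 alone.
  - Other serious: 1 + 15 = 16 days under 6.2.2.6; 15 + 15 = 30 days under 7.2 alone.

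The 8 and 14 days use a clock that 6.2.2.6 starts at receipt. The 16 and 30 days need one assumption, because that clock starts at the sponsor's determination and the documents give no time for that step. I assume determination on the day of receipt. If it takes d days, the figures become 16 + d and 30 + d; the difference stays 14 days provided d is the same either way.

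**3. The non-serious line.**

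The 24-hour rule covers SAEs only, so a line about non-serious events cannot conflict with it. The line does conflict with the opening sentence of 7.2, which sends unanticipated AEs to the IRB and sponsor with no limit on seriousness. Collection is not affected: 6.2.2.4 and 6.2.2.5 still put these events on the CRF.

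**The case against.** The best defence is that both limits are upper bounds. A site that reports within 24 hours also meets 7 or 15 days, so one action satisfies both sections, and nothing in 7.2 expressly overrides 6.2.2.6.

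The content of the 7.2 report also suggests a later, fuller document. It must explain why the event was judged unanticipated and describe protocol changes or corrective actions taken or proposed, including changes by the sponsor, which presupposes that the sponsor already knows. Protocol 6.2.2.3 makes the sponsor's medical monitor responsible for judging expectedness, which again needs the event to have arrived first.

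Much of this stands. Any delay is conditional, and the two-report sequence is a plausible intention. But 7.2 does not state it. It names the sponsor as recipient and presents its limits as the timeline that meets the need for prompt reporting. Protocol 6.2.2.7, by contrast, refers explicitly to 6.2.2.6 for SAEs found at the last contact, so the protocol does cross-refer elsewhere.

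A reader might also infer three stronger points that the documents do not support:

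- **Late DMC review.** The DMC reviews safety data under Protocol 10.5, but SAP 2.2 leaves the timing of its analyses to a charter that is not among these documents. No text ties DMC review to the 7.2 report.
- **Loss of non-serious safety data.** These events are exempt from a separate report, not from recording. Protocol 11.1 sends all data to the sponsor, and SAP 9.3 summarises treatment-emergent events by arm.
- **Thirty days as an outer limit.** It is not one, because the time to the sponsor's determination is unstated.

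**Conclusion.** The concern holds as a conflict between two stated sponsor deadlines: 24 hours in 6.2.2.6 against 7 or 15 days in 7.2. The possible extra time to sponsor receipt is up to 6 days for fatal or life-threatening events and 14 days for other SAEs. It arises only at a site that relies on 7.2 and passes over the unconditional 24-hour rule. The onward effect on FDA notice also applies only to events that qualify for expedited reporting. The figures for other serious events rest in addition on same-day sponsor determination.

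A separate and smaller inconsistency lies within 7.2, between its opening sentence and its exemption of non-serious events.

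No endpoint, analysis population, sample size, error rate or planned safety summary is affected. The correction is still worth making, because it concerns prompt notice of serious, unexpected and possibly related events and costs almost nothing.

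**What to change.** Reconcile the two sections in the next amendment or a clarification letter to sites:

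1. In 7.2, remove the sponsor as recipient from the 7-day and 15-day lines, so that they govern reporting to the IRB only.
2. Add a sentence to 7.2 that initial reporting of every SAE to the sponsor, unanticipated or not, follows 6.2.2.6, and that any 7.2 report to the sponsor is additional.
3. In the 7-day line, join fatal and life-threatening with 'or', as 6.2.2.6 does.
4. Align the opening sentence of 7.2 with its exemption for non-serious events, so that the section gives one answer on whether those events need a separate report. The CRF requirement in 6.2.2.5 needs no change.

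The cost is drafting and circulation to sites. No procedure, visit or analysis is added.

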7.3 Reporting Unanticipated Adverse Events to Participants

Revance will disclose clinical trial data to individuals, to investigators at clinical sites, and publicly as aggregate summaries, in accordance to Regulatory and local legal requirements.

Version 6 xx June 2020

9 STATISTICAL PLAN

This section contains a brief overview of the statistical analyses planned for this study. A formal statistical analysis plan (SAP) will be finalized before database lock.

9.1 Sample Size

The sample size calculation is based on the effect size that was observed for the primary endpoint (change from baseline in MAS in the SMG) from the registration study of Dysport (Gracies J, 2015) for the treatment of ULS.

9.2 Analysis Populations

• Intent-to-Treat Population: Efficacy analysis will be performed using the intention-to-treat analysis set. This population includes all subjects randomized, given one injection session of the study medication and have a MAS score in the SMG at baseline and 6 weeks after treatment and a PGIC score at least one post-baseline MAS assessment.

- Pre-COVID-19 ITT Population: a subset of the ITT population, subjects who were enrolled before COVID-19 enrollment hold (20MAR2020).
- Pre-COVID-19 PP Population: a subset of the PP population, subjects who were enrolled before COVID-19 enrollment hold (20MAR2020).

9.2.1. Primary Analyses

Efficacy analysis will be performed using the intention-to-treat analysis set. This population includes all subjects randomized, given one injection session of the study medication and have a MAS score in the SMG at least one post-baseline MAS assessment.

10 SUPPORTING DOCUMENTATION AND OPERATIONAL CONSIDERATIONS

10.1 Good Clinical Practice

It is the responsibility of the Principal Investigator to oversee the safety of the subject at their site. The Investigator will ensure that this study is conducted in full compliance with the principles of the "Declaration of Helsinki" (as amended in Tokyo, Venice, Hong Kong, and South Africa), ICH guidelines, or with the laws and regulations of the country in which the research is conducted. By signing the US Form FDA 1572, "Statement of Investigator", the Investigator commits to adhere to applicable sections of the US 21CFR parts 50 "Protection of Human Subjects", 54 "Financial Disclosure by Clinical Investigators", 56 "Institutional Review Boards", and 312 subpart D "Responsibilities of Sponsors and Investigators". All Investigators will ensure adherence to ICH guidelines for GCP and Clinical Safety Data Management.

